7.3.3. Analgesic use

Protocol-specified analgesics (see section 7.2.4) for endometriosis-related pain will be analyzed. Proportion of patients not using protocol-specified opioids for endometriosis-associated pain at Week 52, and Week 104/EOT will be presented by pivotal phase 3 study treatment group and by visit. Proportion of patients not using protocol-specified analgesics for endometriosis-associated pain at Week 52, and Week 104/EOT will be presented by pivotal phase 3 study treatment group and by visit. Two-sided 95% CIs for the proportions will be generated based on Clopper-Pearson exact binomial.

7.3.4. Change from Baseline in Patient Global Assessments

The PGAs for overall pelvic pain and function impairment use a 5-point response scale. To calculate change from pivotal phase 3 studies baseline to Week 52, and Week 104, the numerical scores shown in Table 18 Table 1 will be assigned to each response level.

Table 18: Patient Global Assessment Numerical Scores

Function	Overall Pelvic Pain	Numerical Score
Not at all	Absent	0
Minimally	Mild	1
Moderately	Moderate	2
Significantly	Severe	3
Very Significantly	Very Severe	4

The number and percentage of patients in each severity of PGA category will be presented by pivotal phase 3 study treatment group. The mean change of total PGA score from pivotal phase 3 study Baseline will be presented for overall pelvic pain and function separately by visit and by pivotal phase 3 study treatment group. LS means and 95% CI are based on mixed-effects model with visit, pivotal phase 3 study treatment group, treatment-by-visit interaction, region (North America, Rest of World), time since initial surgical diagnosis of endometriosis (< 5, \geq 5 years), and baseline value included as fixed effects; The multiple visits for each patient are the repeated measures as random effects within each patient, and an unstructured covariance matrix is assumed. Here treatment refers to pivotal phase 3 study treatment group. Least squares mean and 95% CI will be presented by pivotal phase 3 study treatment group and by visit. The categorical changes of amount of improvement of PGA for overall pelvic pain from baseline to Week 52, and to Week 104 will be summarized by pivotal phase 3 study treatment group and by

visit. Proportion of patients with PGA for function Improvement, No Change, and Worsening from Baseline will be presented by pivotal phase 3 study treatment group and by visit.

7.3.5. Change from Baseline in Functional Impairment on sB&B Scale

The daily eDiary completed by patients includes assessments of endometriosis-associated pain by the sB&B scales for DYS, pelvic pain, and dyspareunia. The dysmenorrhea and dyspareunia scales have possible scores of 0 to 4, while the pelvic pain scale has possible scores of 0 to 3, as outlined in Table 19.

Table 19: Subject Modified Biberoglu and Behrman Scales for Dysmenorrhea, Pelvic Pain, and Dyspareunia

Dysmenorrhea	Pelvic Pain	Dyspareunia	Numerical Score
No pain	No pain	No pain	0
Mild	Mild	Mild	1
Moderate	Moderate	Moderate	2
Severe	Severe	Severe	3
Did not Menstruate	--	No Intercourse	4

The mean sB&B for DYS during the Week 52, Week 104/EOT pain assessment period will be the average over the days when the DYS response was something other than “Did not menstruate.” If the patient reports “Did not menstruate” for all days of the pain assessment period, then the mean sB&B score will be imputed as 0.

The mean sB&B for NMPP during the Week 52, Week 104/EOT pain assessment period, derived from the sB&B for pelvic pain, will be the average of the scores reported for days on which a patient reports she did not menstruate. Mean change of sB&B for NMPP and percent change from baseline will be presented by visit by treatment group.

The mean sB&B for dyspareunia during the Week 52, Week 104/EOT pain assessment period will be the average over the days when the dyspareunia response was something other than “No intercourse.” Mean change of sB&B for dyspareunia and percent change from baseline will be presented by visit by pivotal phase 3 study treatment group. Additionally, the following will be summarized for patients who reported one or more day on which they had vaginal sexual intercourse during a given time interval; the percentage of patients whose maximum dysmenorrhea score was severe, moderate, mild, and none during the specified time interval; the percentage of patients whose maximum dysmenorrhea score was severe or moderate and mild or none during the specified time interval.

The mean change and percent change of sB&B score from baseline to Week 52, and to Week 104/EOT will be presented by visit and by the pivotal phase 3 study treatment group for DYS, NMPP, and dyspareunia separately. LS means of mean change and 95% CI are based on mixed-effects model with visit, pivotal phase 3 study treatment group, treatment-by-visit interaction, region (North America, Rest of World), time since initial surgical diagnosis of endometriosis (< 5, >=5 years), and baseline value included as fixed effects. The multiple visits for each patient are the repeated measures as random effects within each patient, and an unstructured covariance

matrix is assumed. Here treatment refers to pivotal phase 3 study treatment group. Least squares mean and 95% CI will be presented by pivotal phase 3 study treatment group and by visit.

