4.5. Handling Multiple Values on the Same Day

Questionnaires

If a questionnaire (eg, PGA, PGIC, or EHP-30) is completed multiple times on the same day, then the questionnaire assessment with the worst score will be used for analysis.

eDiary Entries

If there are multiple eDiary entries (NRS, sB&B) on the same day for a patient, then the worst score (eg, higher pain score) will be used for analysis.

If there are multiple eDiary entries (analgesics) reported on the same day but at different time for a patient, then all pills reported at different time will be used for analysis. If there are multiple eDiary entries (analgesics) on the same day and at the same time, then the record with the last modified time will be used for that time.

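### SAP Section 7.3.5 names dysmenorrhea instead of dyspareunia in the extra sB&B severity summary, and no rule keeps the non-event code 4 out of maximum and worst-score steps

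*SAP*

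**What the plan says.** SAP Section 7.3.5 defines the mean sB&B dyspareunia score for the pain assessment period as "the average over the days when the dyspareunia response was something other than" the no-intercourse response. In the same paragraph it adds a further output, to be "summarized for patients who reported one or more day on which they had vaginal sexual intercourse during a given time interval". Two tabulations follow for that group. One is four-level: "the percentage of patients whose maximum dysmenorrhea score was severe, moderate, mild, and none during the specified time interval". The other is two-level: "the percentage of patients whose maximum dysmenorrhea score was severe or moderate and mild or none during the specified time interval".

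On the scoring itself, the section states: "The dysmenorrhea and dyspareunia scales have possible scores of 0 to 4, while the pelvic pain scale has possible scores of 0 to 3". In Table 19 the pain responses run from 0 (no pain) to 3 (severe). The code 4 belongs to "Did not Menstruate" on the dysmenorrhea scale and to the no-intercourse response on the dyspareunia scale. The pelvic pain scale has no code 4.

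For several sB&B or NRS diary entries on one day, Section 4.5 says "then the worst score (eg, higher pain score) will be used for analysis".

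**The concern.** There are two linked defects in the rules.

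First, the restriction to patients with intercourse makes sense for dyspareunia, yet the variable tabulated is dysmenorrhea. Because the word appears in both clauses, a programmer has no correct instance to infer from. The output would describe period pain in sexually active women, which Table 1 of the SAP does not list as an endpoint. The distribution of worst sB&B dyspareunia severity would not be produced.

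Second, the responses with code 4 record that there was nothing to rate, but they carry the highest number on the scale. The exclusion is written for the means only. A maximum, or a same-day rule that takes the higher score, has no written instruction on what to do with them.

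**Working it through.** The plan states no figure on this point, so there is none to reproduce. The check sets the rules side by side and puts the Table 19 codes through them.

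**1. Which scale the sentence belongs to.**
- Position: it follows directly on the mean, mean change and percent change for dyspareunia in Section 7.3.5.
- Denominator: patients with one or more days of intercourse.
- Variable named: dysmenorrhea, in both versions.
- Table 1: the sB&B dyspareunia endpoint is change and percent change in the mean. No dysmenorrhea endpoint is conditional on intercourse.

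Position and denominator point to dyspareunia, and only the variable disagrees.

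**2. What else covers sB&B dyspareunia.** Section 7.3.5 otherwise gives means, mean and percent changes, and least-squares means. None of these is a distribution of maximum severity. Dyspareunia also appears on the NRS (Section 7.3.2) and the PGIC (Section 7.3.6), but those are different instruments.

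**3. The maximum on a purely numeric reading.** Take an assumed 35-day period with five event days scored 1, 1, 0, 1, 0 and 30 days coded 4.
- Maximum over all codes = 4, which is none of the four categories.
- Maximum over pain scores only = 1 (mild).
- Mean over pain scores only = 3/5 = 0.6, as the mean rule already gives.

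One code-4 day is enough to make the numeric maximum 4. If each day independently has probability q of code 4 (q is assumed; the SAP gives no such figure), then P(at least one in 35 days) = 1 − (1 − q)^35:
- q = 0.05: 0.834
- q = 0.10: 0.975
- q = 0.50 or more: about 1.000

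Changing the word to dyspareunia does not remove this, because a single day without intercourse also carries code 4. The two corrections are therefore both needed.

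**4. The same-day rule on a numeric reading.** For a pain score a of 0, 1, 2 or 3 duplicated with code 4, max(a, 4) = 4 in every case, and the mean rule then drops the day. Example: three event days scored 3, 1, 1, the first duplicated with code 4.
- Pain score kept: (3 + 1 + 1)/3 = 1.67.
- Code 4 kept, day dropped: (1 + 1)/2 = 1.00.

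**5. What a recode must preserve.** Section 7.3.5 sets the mean dysmenorrhea sB&B score to 0 when every day of the period is reported as not menstruating. If that response were recoded to plain missing, such a patient could not be told apart from one with no diary entries, and the zero rule could not be applied. The response has to remain identifiable.

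**The case against.** The best defence is that little is lost. The listed dyspareunia sB&B endpoint is the mean, which excludes the no-intercourse response and has its own mixed model. The maximum-severity table is introduced as an addition and appears in no row of Table 1. All analyses are descriptive, without formal comparisons. This stands, and it limits the weight of the point. A reader might infer that a listed secondary endpoint is not produced; Table 1 and Section 7.3.5 show that it is.

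On code 4, the defence is that the summary is defined by labels (severe, moderate, mild, none), that neither non-event response is among them, and that the gloss in Section 4.5 speaks of a higher pain score. A reader might infer that practically every patient would fall outside the tabulated categories, or that the worst-score rule deletes the worst pain. Both follow only if code 4 is treated as an ordinary number, and the labels and the gloss point away from that. The probabilities in step 3 show how far a literal program would go wrong; they do not predict what will be reported. What remains is a missing rule.

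A reader might also infer that every patient amenorrheic through the interval drops out of the table. The SAP does not settle this. Section 7.1.1 keeps missing as a category in the denominator by default, while Section 4.1 uses non-missing denominators for by-visit observed data. The question arises only while the table is about dysmenorrhea.

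None of this answers the wrong scale name, for which the SAP gives no rationale.

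**Conclusion.** The point holds, and its core is the wrong scale. In both versions the additional Section 7.3.5 summary tabulates dysmenorrhea where the paragraph and the denominator call for dyspareunia, so as written no distribution of maximum sB&B dyspareunia severity is produced. This is certain from the text.

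The code-4 part is a gap in the rules: exclusion is stated for the means and left unstated for the maximum and for same-day selection. The damage depends on a literal numeric reading that the plan's own labels make unlikely. The same-day effect also needs conflicting duplicate entries on one day, whose frequency the SAP does not give, and it is probably small.

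The affected outputs are descriptive secondary summaries. The mean dyspareunia and dysmenorrhea sB&B scores are touched only through such duplicates, and the primary responder endpoints not at all. The correction should be made, but nothing in the main conclusions turns on it.

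**What to change.** 1. In Section 7.3.5, replace dysmenorrhea with dyspareunia in both the four-level and the two-level clause.
2. Add a footnote to Table 19: pain scores run from 0 to 3 on all three scales, and code 4 marks a response to which no pain score applies.
3. State in Section 7.3.5 that these responses are excluded from the maximum-score summary, and in Section 4.5 that for sB&B a same-day pain score is kept over code 4.
4. Keep the raw response, flagged as not applicable and not set to missing, so that the zero rule for the mean dysmenorrhea score still works.

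The cost is a few lines of SAP text and an exclusion flag in the programs. No new data are needed. The SAP's introduction allows amendment before database lock.

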7.3.6. Patient Global Impression of Change

The PGICs completed by patients includes assessments of DYS, NMPP, and dyspareunia use a 7-point response scale. The following possible responses are: Much better, Better, A little better, The same, A little worse, Worse, or Much worse. The proportion of patients who are better or much better on the PGIC at Week 52 and two-sided 95% CI based on Clopper-Pearson exact binomial will be presented by pivotal phase 3 study treatment group for DYS, NMPP, and dyspareunia separately. Number and percentage of patients in summary of PGIC category will be presented by pivotal phase 3 study treatment group for DYS, NMPP, and dyspareunia separately.

7.4. Exploratory Efficacy Endpoints

Descriptive summaries by pivotal phase 3 study treatment group and mean change from baseline will be provided for the following exploratory endpoints.

For final analysis, the following exploratory endpoints will be assessed:

- Change from Baseline to Week 24, Week 52, Week 104 in the EHP-30 scale total score
- Change from Baseline to Week 24, Week 52, Week 104 in the EHP Work Domain score

Change from Pivotal phase 3 Studies Baseline to Week 24, Week 52, Week 104 in the EQ-5D-5L

7.4.1. Exploratory Efficacy Analyses

EHP-30 Total Score

The total score for the EHP-30 questionnaire will be calculated and analyzed as a normalized score using the formula above. Total score will be summarized by visit by pivotal phase 3 study treatment group. Score change with 95% CI from pivotal phase 3 studies baseline to Week 24, Week 52, or Week 104 will be summarized by pivotal phase 3 study treatment group.

A mixed-effects model with repeated measures will be used to assess total score change for the EHP-30 at Week 24, Week 52 and Week 104. The model will have baseline value, visit, treatment, treatment-by-visit interaction, region (North America, Rest of World), time since initial surgical diagnosis of endometriosis (< 5 , ≥ 5 years) included as fixed effects.

Visit is also included in the model as random effect within each patient and an unstructured variance-covariance matrix is assumed. If the mixed-effects model fails to converge, a first-order autoregressive variance-covariance matrix will be used. Here treatment refers to pivotal phase 3 study treatment group. Least squares mean and 95% CI will be presented by pivotal phase 3 study treatment group and by visit.

EHP Work Domain

The score for the 5-item EHP work domain questionnaire is calculated by adding the scores for

individual items (each with five response options scored from 0 to 4) to obtain a total raw score, then dividing by 20 and multiplying the result by 100 to obtain a normalized score that ranges from 0 to 100. The normalized score used for analysis is:

$$\text{Normalized score} = (\text{Total raw score} / 20) \times 100$$

Higher scores represent a greater (ie, more negative) impact of endometriosis on work-related activities. If one or more items are missing, then the score cannot be calculated for that patient and will be set missing.

The normalized score for the EHP-30 work domain will be summarized by visit and by pivotal phase 3 study treatment group. Score change from studies baseline to Week 24, Week 52, and Week 104 will be summarized by pivotal phase 3 study treatment group.

A mixed-effects model with repeated measures will be used to assess total score change for the EHP work domain at Week 24, Week 52 and Week 104. The model will have baseline value, visit, treatment, treatment-by-visit interaction, region (North America, Rest of World), time since initial surgical diagnosis of endometriosis (< 5, >= 5 years) included as fixed effects. Visit is also included in the model as random effect within each patient and an unstructured variance-covariance matrix is assumed. If the mixed-effects model fails to converge, a first-order autoregressive variance-covariance matrix will be used. Here treatment refers to pivotal phase 3 study treatment group. Least square means and associated 95% CIs will be presented by treatment and visit.

For each question, the proportion of patient in each category of the work domain will be presented at Baseline, week 24, Week 52 and Week 104 by pivotal phase 3 study treatment group. Additionally, the proportion of patients shifting from “often/always” to “never/rarely” from Baseline to Week 24, from Baseline to Week 52, and from Baseline to Week 104 will be described by visit and by pivotal phase 3 study treatment group.

European Quality of Life Five-Dimension Five-Level Scale

The EQ-5D-5L is a standardized instrument for use as a measure of health outcomes. Mobility, self-care, usual activities, pain/discomfort, and anxiety/depression are each assessed on a 5-level categorical scale. The categorical changes of amount of improvement (1-4 categories), amount of deterioration (1-4 categories), or no change from baseline to Week 24, Week 52, and Week 104 will be summarized by pivotal phase 3 study treatment group. The EQ-5D-5L also has an assessment of overall health status that the patient rates on a 100-point visual analogue scale. The change from baseline to Week 24, Week 52, and Week 104 for the visual analogue scale scores will be summarized by pivotal phase 3 study treatment group.

8. PHARMACODYNAMIC ANALYSES

For pharmacodynamic assessment, data for the extension study consists of predose concentrations of serum estradiol. The change from the pivotal phase 3 study Baseline to Week 52 and to Week 104 in predose concentrations of serum estradiol will be summarized. This data will be listed and summarized using descriptive statistics (including raw and change from pivotal phase 3 study Baseline to Week 52 and Week 104 by pivotal phase 3 study treatment group, and by visit).

For pharmacodynamic assessment, the number and percentage of patients with individual E2 concentration values will be summarized by pivotal phase 3 study treatment group (relugolix + E2/NETA, relugolix + delayed E2/NETA, or placebo) and visit according to the following categories:

- < 10 pg/mL, 10 to < 20 pg/mL, 20 to < 30 pg/mL, 30 to < 40 pg/mL, 40 to < 50 pg/mL, 50 to < 60 pg/mL, 60 to < 70 pg/mL, and \geq 70 pg/mL
- < 20 pg/mL, 20 to < 50 pg/mL, and \geq 50 pg/mL
- < 20 pg/mL, 20 to < 60 pg/mL, and \geq 60 pg/mL

9. SAFETY ANALYSES

Unless otherwise specified, safety analyses will be conducted using the Extension Safety Population according to the actual treatment received by the patients in the extension study.

Safety assessments will include treatment-emergent adverse events, vital signs, clinical laboratory tests, 12-lead ECG, bone mineral density with DXA, mammograms (for women who are or become \geq 40 years of age during the study), and endometrial biopsy.

9.1. Adverse Events

Adverse events will be collected from the time of the first dose of open-label study drug through the safety Follow up visit approximately 30 days after the last dose of open-label study drug (the end of extension treatment period), or the date of initiation of another investigational agent or hormonal therapy or surgical intervention affecting the hypothalamic-pituitary-gonadal axis or surgical intervention for endometriosis, whichever occurs first, as also specified in the Schedule of Activities in the study protocol Section 1.1. Additionally, serious adverse events reported to the investigator after the safety reporting period should be reported to the sponsor regardless of causal relationship to study drug treatment.

Using a Safety Report Form, all serious adverse events must be reported within 24 hours of the study site personnel's knowledge of the event, regardless of the investigator assessment of the relationship of the event to study drug.

The severity of all treatment-emergent adverse events will be evaluated by the investigator based on the National Cancer Institute's Common Terminology Criteria for Adverse Events (CTCAE, version 5.0 dated 27 Nov 2017), and will be coded to preferred term and system organ class using MedDRA 22.0 or higher.

A treatment-emergent adverse event is defined as any adverse event that occurs after administration of the first dose of pivotal phase 3 study drug.

Adverse event summaries will be based on treatment-emergent adverse events in the pivotal phase 3 and extension studies, unless otherwise specified. All adverse events in the pivotal phase 3 and extension studies will be listed in by-patient listings.

The following tabular summaries that include the number and percentage of patients will be provided:

- Overview of adverse events;
 - Safety parameters of interest

- Safety parameters of interest with first onset during extension study
- All adverse events;
 - By SOC and PT;
 - By decreasing frequency of PT;
 - By SOC, PT, and maximum severity;
 - Study drug-related per investigator by SOC and PT;
 - By time to onset (Day 1 to Week 24, > Week 24 to Week 52, >Week 52 to Week 78, > Week 78 to Week 104, > Week 104), SOC and PT;
 - Exposure-adjusted AE rate by SOC and PT
- Adverse events reported in at least 5% of patients in any treatment group
 - By decreasing frequency of PT;
- Grade 3 or above adverse events;
 - By SOC and PT;
 - By decreasing frequency of PT;
 - Study drug-related per investigator by SOC and PT;
 - First onset events during extension study by decreasing frequency of PT
- Adverse events leading to study drug withdrawal;
 - By SOC and PT;
 - By decreasing frequency of PT;
- Adverse events leading to dose withdrawal with first onset during extension study;
 - By SOC and PT;
 - By decreasing frequency of PT
- Adverse events resulting in fatal outcome;
 - By decreasing frequency of PT;
- Serious adverse events;
 - By SOC and PT;
 - By SOC, PT and maximum grade
 - By decreasing frequency of PT;
 - By SOC, PT, and relationship to study drug;
- Adverse events of clinical interest (ALT or AST $\geq 3 \times$ ULN);
 - By SOC, PT, and maximum severity;

- By decreasing frequency of PT.
- First onset events during extension study by PT
- Resolved while on study drug treatment (ie, prior to the last dose date)
- Adverse events with first onset during the extension study;
 - By SOC and PT;
 - By decreasing frequency of PT;
- Serious adverse events with first onset during the extension study;
 - By SOC and PT;
- Mood disorder event with first onset during the extension study;
 - By decreasing frequency of PT;
 - Resolved while on study drug treatment (ie, prior to the last dose date)
- Vasomotor symptoms with First Onset During the Extension Study
 - By SOC and PT;
 - By decreasing frequency of PT;
 - Resolved while on study drug treatment (ie, prior to the last dose date)
- Bone health related events
 - By decreasing frequency of PT;
 - First onset events during extension study by PT;
- Hepatic transaminase elevations
 - By decreasing frequency of PT;
 - First onset events during extension study by PT;
- Carbohydrate and lipid metabolic effects
 - By decreasing frequency of PT;
 - First onset events during extension study by PT;

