4. GENERAL CONSIDERATIONS FOR DATA ANALYSES AND HANDLING OF MISSING DATA

4.1. Data Presentation Conventions

All statistical analyses will be conducted using SAS[®] Version 9.2 or higher. Only descriptive analyses will be provided. Formal statistical comparisons are not planned.

All confidence intervals (Cis) will be reported as two-sided 95% Cis unless otherwise stated.

Where appropriate, variables will be summarized descriptively by study visit. For the categorical variables, the count and proportions of each possible value will be tabulated by pivotal phase 3 study treatment group. For continuous variables, the number of patients with non-missing values, mean, median, standard deviation (SD), minimum, and maximum values will be tabulated.

Unless otherwise specified, the following conventions will be applied to all analyses:

- Mean and median values will be formatted to one decimal place, unless otherwise specified. For BMD DXA, mean and median values will be formatted to two decimal places. Standard deviation values will be formatted to two more decimal places, unless otherwise specified. Minimum and maximum values will be presented to the same number of decimal places as the measured value. If the measured value is large (eg, > 100), fewer decimal places may be displayed.
- Percentages will be rounded to one decimal place.
- P values will be rounded to four decimal places. P values < 0.0001 will be presented as "< 0.0001" and p values > 0.9999 will be presented as "> 0.9999".
- 1 month = 30.4375 days. Month is calculated as (days/30.4375) rounded to one decimal place.
- 1 year = 365.25 days. Year is calculated as (days/365.25) rounded to one decimal place.
- Age will be calculated using the date of randomization in pivotal phase 3 study. If only year of birth is collected, 1 July of the year of birth will be used to calculate age.
- 1 pound = 0.454 kg.
- 1 inch = 2.54 cm.
- Missing efficacy or safety data will not be imputed, unless otherwise specified.
- For laboratory results above or below sensitivity limits displayed as "<" or ">" a quantification threshold, 0.000000001 will be subtracted or added, respectively, to the threshold to derive a numeric result for analysis.
- For safety analyses, percentages will be calculated based on the number of patients in the analysis population in each pivotal phase 3 study treatment group.

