4.2.2. Extension Safety Population

The Extension Safety population is defined as all enrolled patients who received any amount of open-label study drug in MVT-601-3103. Any patient who received at least one dose of relugolix will be considered as a relugolix patient for purposes of safety analyses, consistent with analysis in the pivotal phase 3 studies. All safety analyses will be performed on the Extension Safety population, unless otherwise specified. Safety data will be analyzed by pivotal phase 3 study treatment group according to the actual treatment received (not the randomized treatment) in pivotal phase 3 study.

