5. STUDY POPULATION

5.1. Subject Disposition

The number and percentage of patients for each of the following categories will be summarized by pivotal phase 3 study treatment group in final analysis:

- All patients enrolled defined as taking the first dose of study drug in the Extension Study;
- Patients included in the Extension Study population;
- Patients included in the Extension Safety population.

In final analysis, the number and percentage of patients for each of the following categories will be summarized by pivotal phase 3 study treatment group:

- Patients who completed 52 weeks treatment (24 weeks pivotal study treatment period and 28 weeks open-label treatment period)
- Patients who completed the 104 weeks of treatment (24 weeks pivotal study treatment period and 80 weeks open-label treatment period);

- Patients who discontinued early from the 80 weeks open-label treatment period and reasons for discontinuation;
- Patients who entered the BMD post-treatment Follow-Up period.

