9.1.8. Exposure-adjusted Adverse Events

Adverse events by time to onset and an exposure-adjusted adverse event analysis will be provided. The exposure-adjusted adverse event rate will be summarized by system organ class and preferred term for each pivotal phase 3 study treatment group, where the exposure-adjusted adverse event rate is calculated as number of patients with a particular adverse event by total exposure-time among patients at risk of an initial occurrence of the event. Exposure-time is derived as exposure to any study drug throughout the pivotal phase 3 studies and extension study.

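### The adverse event time-to-onset table divides by the full safety population, so its percentages after Week 52 are understated once women stop treatment

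*SAP*

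**What the plan says.** Section 9.1 introduces its adverse event tables with "The following tabular summaries that include the number and percentage of patients will be provided". One of them is "By time to onset (Day 1 to Week 24, > Week 24 to Week 52, >Week 52 to Week 78", followed by >Week 78 to Week 104 and >Week 104. The section states no denominator for it.

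Section 4.1 supplies the default, which holds unless another rule is specified: "For safety analyses, percentages will be calculated based on the number of patients in the analysis population in each pivotal phase 3 study treatment group". Section 4.2.2 defines that population as "all enrolled patients who received any amount of open-label study drug in MVT-601-3103", with no condition on how long the drug was taken.

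Section 9.1 has adverse events collected "through the safety Follow up visit approximately 30 days after the last dose of open-label study drug", or until certain other treatments begin if that is sooner. Section 5.1 foresees dropout and reports "Patients who discontinued early from the 80 weeks open-label treatment period and reasons for discontinuation".

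Section 9.1.8 says "Adverse events by time to onset and an exposure-adjusted adverse event analysis will be provided". The exposure-adjusted rate is given by system organ class and preferred term for each group, over exposure in both studies together. It is not split by onset interval.

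**The concern.** A woman who stops at Week 40 leaves routine adverse event collection at about Week 44. Under the Section 4.1 rule she still counts in the denominators for >Week 52 to 78, >Week 78 to 104 and >Week 104. Those columns then mix the risk in women being observed with the fraction of women who have left.

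This matters because the safety objective in Section 1.1 covers treatment for up to 104 weeks, and this is the only adverse event table listed in Section 9.1 that divides the extension into successive periods. A reader asking whether risk changes with longer treatment will look here. With any dropout, a steady late risk prints as a falling one and a modest late rise can print as flat.

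**Working it through.** **A figure to reproduce.** The SAP states no adverse event rate and no dropout rate. Its only size figure is about 800 patients, given as 67% of 1200 (Section 2.2): 0.67 × 1200 = 804, which agrees. The check below does not depend on it.

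**Inputs from the SAP.** The intervals are 24, 28, 26 and 26 weeks, then a short period after Week 104. Everyone completed 24 weeks in a pivotal study, so retention is taken as 100% at Week 24.

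**Assumptions.** The risk is a constant 10% per 26 weeks under observation. Total dropout D over Weeks 24 to 104 is 20%, 30% or 40%, and linear. The roughly 30 days of observation after last dose are ignored at first.

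**Formulas.**
- Share still on treatment at week t: S(t) = 1 − D × (t − 24)/80.
- With linear dropout, the mean share over an interval is S at its midpoint (Week 65 or Week 91).
- Printed percentage = 10% × mean share.
- Percentage on patients present at the interval's start = printed percentage / S(start).

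For D = 40% and >Week 78 to 104: the mean share is 1 − 0.40 × 67/80 = 0.665, so the table prints 6.65%. S(78) = 1 − 0.40 × 54/80 = 0.73, and 6.65/0.73 = 9.11%.

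| Interval | D | Share at start | Mean share | Printed, full group | On patients present at start |
|---|---|---|---|---|---|
| >52 to 78 | 20% | 0.930 | 0.898 | 8.98% | 9.65% |
| >52 to 78 | 30% | 0.895 | 0.846 | 8.46% | 9.46% |
| >52 to 78 | 40% | 0.860 | 0.795 | 7.95% | 9.24% |
| >78 to 104 | 20% | 0.865 | 0.833 | 8.33% | 9.62% |
| >78 to 104 | 30% | 0.798 | 0.749 | 7.49% | 9.39% |
| >78 to 104 | 40% | 0.730 | 0.665 | 6.65% | 9.11% |

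These two intervals are equally long, so the fall between them comes from dropout alone. After Week 104 essentially only completers are observed, so that column is low by about the whole dropout fraction.

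**Masking.** To print 10% in >Week 78 to 104, the true risk would have to be 10/0.833 = 12.0% at 20% dropout, or 10/0.665 = 15.0% at 40%.

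**Second dropout model.** With exponential dropout, the >Week 78 to 104 column prints 8.3%, 7.4% and 6.5% for 20%, 30% and 40%. The whole row at 30% reads 9.3%, 10.1%, 8.3% and 7.4%. With no dropout it reads 9.3%, 10.7%, 10.0% and 10.0%, so the early rise comes from unequal interval lengths.

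**The 30-day tail.** If observation runs 30/7 = 4.3 weeks past the last dose at the same risk, the mean share at D = 40% becomes 1 − 0.40 × (67 − 4.3)/80 = 0.687. The column then prints about 6.9% instead of 6.65%.

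**Rate per person-time.** 10% per 26 weeks is 10/26 × 52.18 = about 20 per 100 patient-years. That figure stays flat across intervals at every dropout level.

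**The case against.** The strongest reply is that this is one descriptive table. The primary objectives are responder rates, no interval comparison or test is planned, and the safety endpoint is overall incidence, which the overall tables serve. Full-population percentages also answer a legitimate question: what share of enrolled women had an event in that period. The counts are unaffected. Section 5.1 gives completers of 52 and 104 weeks by group, and many tables report first onset during the extension, a period that every woman in the population entered. All of this stands and limits the weight of the point. It does not repair the table: no at-risk number is planned for Week 78, the first-onset tables treat the extension as one block, and the Section 9.1.8 rate is pooled over time.

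Three stronger readings are tempting but unsupported:
- A reader might infer that women who stopped can contribute nothing later. Section 9.1 still takes in serious events reported after the safety period, and Section 9.1.3 analyses later deaths reported before database lock. The point concerns routine collection.
- A reader might infer a steady fall from Day 1. The second interval is the longest and enters with everyone present, so percentages can rise before falling after Week 52.
- A reader might infer that an at-risk denominator alone restores the true risk. At 40% linear dropout it gives 9.1%, not 10%, because women also leave within the interval.

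**Conclusion.** The point holds for the time-to-onset table. Applied as written, Section 4.1 makes the percentages after Week 52 too low relative to the risk in women still under observation. The direction follows from any early stopping combined with the 30-day limit on routine collection.

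The size is not known from the SAP. Under the assumed constant 10% risk per 26 weeks and 20% to 40% linear dropout, the >Week 78 to 104 column would show about 8.3% to 6.6%. At 10% dropout the gap is small: in the exponential model, 9.2% on the full group against 9.8% on patients present at the start.

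A reader might also infer that the whole adverse event analysis is biased. The documents do not support that: the overall incidence tables are a separate matter and need no change. The correction is worth making because the table is the planned view of late onset. The SAP already takes this care elsewhere: Section 9.3.8 bases the interval amenorrhea rate on patients who stayed on treatment throughout the interval.

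**What to change.** In Section 9.1, for the time-to-onset table only, override the Section 4.1 default:

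- Use as denominator the patients still under adverse event observation at the start of each interval, meaning on study drug or within about 30 days of last dose, and print that n in each column.
- Add events per 100 patient-years within each interval. This handles the unequal interval lengths and dropout within an interval, which the new denominator alone does not.
- State whether the table counts first onset or any onset. If first onset, exclude women with an earlier event of the same term from the at-risk set.
- Keep full-population percentages in the overall adverse event tables.

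The cost is a short addition to Section 9.1 and reprogramming of one table from data already collected. The late-interval percentages will look slightly less favourable. Section 1 of the SAP allows amendment before database lock.
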